5.9. Rescue Treatment

Patients who show no clinical response to treatment at the EOT visit, as well as patients with evidence of relapse, i.e. *T.b. gambiense* found in any bodily fluid, or of probable relapse at any time during follow-up will receive NECT, an alternative treatment for HAT, as per usual practice in the investigational centre.

The definition of probable relapse disclosed at the 6-month, 12-month or 18month follow-up visit is provided in Table 1.

Rescue treatment for HAT will not be recorded in the "Concomitant Treatment" section of the eCRF, but will be recorded as a comment on the "End of Study" page with the date of treatment start.

Table 1 – Clinical Management of Patients

Visit	Ideal timing of visit after end of treatment	Success	Probabale success	Probable failure	Proven failure
24 hours after EOT	Within 2 days	• Patient alive with no evidence of trypanosomes in any bodily fluid (54)			 Evidence of trypanosomes in any bodily fluid
3 months	3 months ± 1 week	 Patient alive with no evidence of trypanosomes in any bodily fluid (no lumbar puncture at 3 months unless Investigator suspects a relapse) 	 Any reason leading the Investigator to request an additional follow-up visit 	 Signs or symptoms suggestive of HAT and of treatment failure leading to use of rescue treatment 	 Evidence of trypanosomes in any bodily fluid
6 months	6 months ± 2 weeks	 Patient alive with no evidence of trypanosomes in any bodily fluid and CSF WBC ≤ 20/µL 	 CSF WBC between 20 and 50/µL and additional follow-up visit requested within 1 to 3 months Any reason leading the Investigator to request an additional follow-up visit 	 CSF WBC ≥ 50/µL (36) Neurological signs or symptoms leading to use of rescue treatment 	 Evidence of trypanosomes in any bodily fluid
12 months	12 months ± 4 weeks	 Patient alive with no evidence of trypanosomes in any bodily fluid and CSF WBC ≤ 20/µL 	 CSF WBC > 20/µL and clinically non-significant increase as compared to previous value(s) CSF WBC > 20/µL and < 50/µL and reduced as compared to previous value(s) Any reason leading the Investigator to request an additional follow-up visit within 1 to 3 months 	 CSF WBC ≥ 50/µL Signs or symptoms suggestive of HAT and of treatment failure leading to use of rescue treatment 	 Evidence of trypanosomes in any bodily fluid

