18 months	18 months ± 4 weeks	 Patient alive with no evidence of trypanosomes in any bodily fluid and CSF WBC ≤ 20/µL Patient with no signs of HAT who refuses to undergo lumbar puncture and who, in the opinion of the Investigator, does not require rescue treatment or an additional follow-up visit 	Any reason leading the Investigator to request an additional follow-up visit within 1 to 3 months	 CSF WBC > 20/µL Signs or symptoms suggestive of HAT and of treatment failure leading to use of rescue treatment 	 Evidence of trypanosomes in any bodily fluid

An uncertain outcome may be a discrepancy between the clinical picture and the laboratory findings, or any situation that leads the Investigator and the study team to consider that an additional follow-up visit is required to decide whether or not to provide rescue treatment.

6. Schedule of Study Procedures and Assessments

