9.8. Efficacy Analysis

9.8.1. Primary Efficacy Analysis

Primary Efficacy Endpoint

The primary efficacy endpoint is the. success or failure, at 12 months after the final treatment intake. The patient's treatment will be a success if there is no evidence of trypanosomes in any bodily fluid, and the WBC count in the CSF is $\leq 20/\mu$ L. Patients with no parasitological evidence of relapse, but with a CSF WBC count > 20/µL or who, in the opinion of the Investigator, require rescue treatment, will be considered to be probable relapses and therefore as failures. Death due to any cause or use of rescue medication will be considered as a relapse, i.e. a failure. A patient who attends the follow-up visit at 12 months or later and who

refuses to undergo lumbar puncture, but who has no signs or symptoms of HAT and for whom the outcome was assessed as favourable at the last assessment will be considered as a probable cure, i.e. a success, unless signs of relapse are detected on any assessment up to 18 months.

Primary Analysis

The primary analysis will be performed on the ITT population.

The primary endpoint is the success or failure of treatment, as defined above.

The primary analysis of success or failure will be performed at 12 months of follow-up.

The primary test is an exact test derived from the exact confidence interval (CI) of the success rate at 12 months.

Two sets of statistical hypotheses will be tested simultaneously:

 H_{0A} : the true success rate is equal to or less than 80%, which is considered to be unacceptable.

H_{1A}: the true success rate is greater than 80%.

 H_{0B} : the true success rate is equal to or greater than 92%, which is the target or expected success rate for fexinidazole.

H_{1B}: the true success rate is less than 92%.

If H_{0A} is rejected, then the success rate is significantly greater than 80% and the estimated rate is consistent with a rate of 92%. In this case, H_{0B} is automatically accepted, but not necessarily true.

If H_{0B} is rejected, then the success rate is significantly less than the target of 92%, and the estimated rate is consistent with the unacceptable rate of 80%. In this case, H_{0A} is automatically accepted, but not necessarily true.

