9.8.3. Secondary Efficacy Analyses

- The secondary analysis will be performed on the success rate at month 18.
- determine whether the success rate of treatment with fexinidazole varies depending on the stage of the disease, i.e. stage 1 versus early stage 2 versus late stage 2, using a Fisher exact test to compare the rates observed with the 3 different stages.

If the difference between the 3 stages is significant, then the exact 95% CI of each success rate at 12 months will be calculated, and the stage that is responsible for the heterogeneity will be identified. The stage responsible for the heterogeneity will be separated from the other 2 stages, and the lower limit of the 95% CI of each of the 2 subgroups will be compared to the limit of 75%, which is slight higher than the success rate of melarsoprol at 12 months. A limit lower than 80%, i.e. 75% instead of 80%, was chosen because the sample size in each subgroup will be smaller, which will have an impact on the statistical power of each comparison. The upper limit of the CI of the success rate in patients with stage-1 HAT should be consistent with (greater than or equal to) the rate of 93%, which is the

historical success rate of pentamidine (61). The upper limit of the CI of the success rate in patients with stage-2 HAT should be consistent with the rate of 94%, which is the historical success rate of NECT.

- The correlation between the success rate and the WBC count in the CSF will be estimated using a logistic regression. The WBC count will be a quantitative covariate. Another analysis will be performed using a logistic regression with a random intercept to take into account the centre effect. A trend test will also be performed using the Bartholomew's test. Another analysis will be performed after pooling patients with late stage-2 HAT treated with fexinidazole in the pivotal study with patients in this study. The correlation between the success rate and the baseline WBC count will be adjusted with a logistic regression model using the centre as covariate.
- The time-course of the cumulative rate of definitive failure (from the start
 of treatment to the definitive failure) will be estimated using the KaplanMeier method, and patients lost to follow-up will be considered as
 censures. The success rate at each timepoint will be estimated and
 compared using a Cochran Q-test. The logistic model for repeated
 measures (Glimmix procedure in SAS[®]) will be used to test the time effect

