14.2.3. Collection of Assent from Child

No specific documentation or form will be used to collect assent from children enrolled in the study. Preference will be given to oral explanation in order to adapt the information to the child's level of understanding. Assent is difficult to obtain from children before 14 years of age since they do not clearly understand what benefits and risks entail (62). It is, however, easier for a child to refuse to participate than to accept to comply with a protocol. Refusal may be expressed when the protocol is explained to the child, or it may arise at any time during the course of the study. Indeed, the child is free to refuse, at any time, to undergo any invasive procedure planned in the protocol, even if s/he had initially agreed to participate in the study (62, 63). The child will be informed of this at the start of the study and at other appropriate moments. If the child refuses to undergo an invasive procedure, this will not jeopardise his/her overall participation in the study, provided that treatment compliance is acceptable.

Refusal to give assent will prevail over any other decision on the child's participation in the study.

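### Table 1's month-18 Success entry for a child who refuses lumbar puncture omits the favourable-last-assessment condition that sections 2.2.1, 9.2 and 9.8.1 place on refusers

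*Protocol*

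**What the plan says.** Table 1 in section 5.9 sorts children into Success, Probable success, Probable failure and Proven failure at each visit. The month-18 Success cell has two entries. The first requires a living patient, no trypanosomes and a CSF WBC of at most 20/µL. The second is a "Patient with no signs of HAT who refuses to undergo lumbar puncture and who, in the opinion of the Investigator"; the limiting clause is "who, in the opinion of the Investigator, does not require rescue treatment or an additional follow-up visit". Neither the last CSF count nor the last outcome is mentioned. If the Investigator wants another visit, the child goes to Probable success instead: "Any reason leading the Investigator to request an additional follow-up visit within 1 to 3 months". A measured month-18 count above 20/µL is Probable failure.

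The endpoint and analysis sections treat refusers differently. Section 9.8.1 counts as a probable cure a patient seen at 12 months or later under this description: "refuses to undergo lumbar puncture, but who has no signs or symptoms of HAT and for whom the outcome was assessed as favourable". The favourable result must be the most recent one, and signs of relapse by month 18 overrule it. Sections 2.2.1 and 9.2 carry the same condition for month 12.

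The month-18 outcome is used in the analysis. Section 2.2.2 makes success or failure at each visit up to month 18 the secondary efficacy endpoint, and section 9.8.3 lists first: "The secondary analysis will be performed on the success rate at month 18". Refusal is expressly permitted in section 14.2.3: "the child is free to refuse, at any time, to undergo any invasive procedure planned in the protocol".

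**The concern.** Two rules in one protocol can give the same child different outcomes, and the looser one rewards a missing measurement. A symptom-free child with a raised last count who accepts the puncture and reads 21/µL is a Probable failure. If that child refuses, the same row allows a full Success. The error can only raise the month-18 rate, and the deciding judgement is an Investigator's opinion in an open-label, single-group study.

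At stake is the month-18 success rate and its comparison with earlier visits (section 9.8.3 plans a Cochran Q-test across timepoints). There is also a route to the primary endpoint. Under section 2.2.1, if there is no month-12 puncture, the outcome of a later puncture or physical examination, including one at month 18, prevails.

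**Working it through.** **The plan's own figures.** Inputs from sections 9.1 and 9.8.1: n = 125, success rule at least 109, null rate 0.80, target 0.92, one-sided alpha 0.025, stated power 97.5%.
- Power = P(X ≥ 109 | n = 125, p = 0.92) = 0.978.
- Exact alpha = P(X ≥ 109 | n = 125, p = 0.80) = 0.0243.
- Exact (Clopper-Pearson) lower 95% bound: 80.05% for 109/125 and 79.12% for 108/125.

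The stated design figures reproduce. The scoring question does not change them.

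**Refusal rules side by side**

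| Place | Visit | Condition for a refuser to be a success |
|---|---|---|
| 2.2.1 | Month 12 | No signs of HAT (or another clear cause), and last available assessment favourable |
| 9.2, primary imputation | Month 12 | No signs, no later relapse symptoms, last available assessment favourable; otherwise failure |
| 9.8.1 | 12 months or later | No signs, last assessment favourable, no relapse signs up to month 18 |
| Table 1 | Month 18 | No signs, and Investigator sees no need for rescue or another visit |

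Only the last row lacks the favourable-last-assessment condition.

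**Can an affected child arise?** Yes, by the protocol's own pathway.
1. At month 6, Table 1 places a count between 20 and 50/µL with an extra visit requested under Probable success. At month 12 it does the same for a count above 20 and below 50/µL that has fallen, and for one above 20/µL with a rise judged clinically non-significant. These children need not be rescued.
2. Section 9.8.1 calls a count above 20/µL without parasites a probable relapse and therefore a failure.
3. Take a child with 35/µL at month 12, lower than before, parasite-free and not rescued. Section 9.8.1 gives failure at month 12.
4. At month 18 the child has no signs and refuses the puncture, and the Investigator sees no need for rescue or another visit. Table 1 gives Success.

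**Route to the primary endpoint.** Suppose the raised count was at month 6 and the child refuses at both months 12 and 18. Sections 9.2 and 9.8.1 give failure if that last assessment is not favourable. Under 2.2.1 the month-18 examination outcome prevails, and Table 1 could supply a Success. Section 2.2.1 also scores as failures the month-12 refusers previously assessed as probable relapse, so this route is open to argument rather than certain.

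**Size.** Each affected child moves the month-18 rate by 1/125 = 0.8 points. The protocol gives no number of such refusers, so k below is an assumption, as is the starting point of 115/125 (92.0%) scored as month-18 successes.

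| k rescored as failures | Rate | Exact 95% CI |
|---|---|---|
| 0 | 92.0% | 85.8 to 96.1 |
| 1 | 91.2% | 84.8 to 95.5 |
| 2 | 90.4% | 83.8 to 94.9 |
| 3 | 89.6% | 82.9 to 94.4 |
| 6 | 87.2% | 80.05 to 92.5 |
| 7 | 86.4% | 79.1 to 91.9 |

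On these assumptions, seven such children would be needed to bring the lower bound below 80%. That limit is only a yardstick here, since the protocol sets no decision rule at month 18.

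**The case against.** **The Investigator clause limits the entry.** This stands. A reader might infer that any symptom-free refuser becomes a success whatever the last count was. The text does not support that: the Investigator must judge that neither rescue nor another visit is needed. Counts of 50/µL or more at months 6 and 12 are generally Probable failure, and section 5.9 sends probable relapse to rescue. Section 6.4.4 requires a return visit when a count raises suspicion of relapse, and the note under Table 1 covers disagreement between clinical and laboratory findings. These safeguards narrow the gap without closing it. The clause is an opinion rather than a CSF criterion, and at an unscheduled visit CSF is sampled only if symptoms suggest progression.

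**Table 1 is headed as clinical management, and scoring detail may be left to the SAP.** The heading is as described, but the columns are outcome categories and no other part of the protocol has a month-18 outcome row. If 9.8.1 reaches month 18, it conflicts with Table 1. If it does not, the month-18 rule is looser than the month-12 rule for no stated reason. The committee in section 10.2 can check consistency, but it needs one rule to apply. This is a conflict between stated rules, not an omitted detail.

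**The effect is small and unquantified.** This also stands. A reader might compare it with the roughly 1.2% relapse between months 12 and 18 (1.2% × 125 = 1.5 children) and conclude that two refusers would hide the change the trial must detect. Section 2.2.1 gives that figure as historical support for the 12-month timepoint; no hypothesis or power is attached to detecting it. Nor does the protocol give any refusal rate from which to estimate the number of affected children.

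**Conclusion.** The conflict is real and limited. Table 1 allows, without requiring, a month-18 success for an unrescued refuser whose last CSF WBC was above 20/µL, while 9.8.1 scores that count as a failure. The exposed group is mainly children at 20 to 50/µL. Any error favours success and is worth 0.8 points per child on the month-18 rate, in a number the protocol does not give. It bears first on a secondary analysis with no decision rule; the primary endpoint may be touched through the prevailing-outcome sentence in 2.2.1. The sample size and stated power are unaffected. It should be corrected, but it does not undermine the design.

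**What to change.** For endpoint scoring only, reconcile the month-18 row of Table 1 with sections 2.2.1, 9.2 and 9.8.1. State that a child who refuses lumbar puncture at month 18 counts as a success only if the last available assessment was favourable under the 9.8.1 definition (no trypanosomes, CSF WBC at most 20/µL, no rescue treatment needed or used), and otherwise as a failure. Say that the same rule applies when a month-18 outcome replaces a missing month-12 outcome under 2.2.1.

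This deliberately uses 9.8.1, rather than Table 1's Probable success category, to decide what is favourable for scoring, and the clause should say so. It takes no position on who should be rescued or recalled, so the clinical-management content of Table 1 can stay as it is.

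The cost is one clause, repeated in the SAP's definition of month-18 success, and a reported month-18 rate that may be slightly lower.

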6.1. Timing of Assessments

The timing of assessments is summarised in Table 3 (p 95).

- D-15 to D-1: Patient screening with detection of *T.b. gambiense*, pre-treatment of concomitant helminthiasis and/or malaria, if any, and ECG.
- D-4 to D-1: Baseline assessment, laboratory screening.
- D1 to D10: treatment period.
- D10 to D12: sampling for PK analyses.
- D11: EOT visit.
- D13 to D18: EOH visit; if the end of hospitalisation is extended beyond D18, the EOH visit should be performed on D18 and an additional unscheduled visit should be performed at hospital discharge.
- Additional follow-up visit: at 9 weeks after D1, i.e. D64 to D70, for patients who reach this visit starting in mid-December 2014.
- Follow-up visits: at M3, M6, M12 and M18 see Table 2 Theoretical Schedule of Visits and Acceptable Leeway). The timing of these follow-up visits is calculated from D11 (EOT).

Theoretical schedule of visits	Ideal timing of visits	Acceptable leeway*	
EOT visit	D11 after the Start of Treatment (SOT)	Between D11 and D12 after SOT	
	(D1 after EOT)	(D1 or D2 after EOT)	
EOH visit	Between D13 and D18 after SOT (D3 and D8 after EOT)	D18 at the latest	
Week 9 after D1	D64 to D70		
3 months	3 months ± 1 week after EOT	2-4 months after EOT	
6 months	6 months ± 2 weeks after EOT	5-9 months after EOT	
12 months	12 months ± 4 weeks after EOT	10-16 months after EOT	
18 months	18 months ± 4 weeks after EOT	17-21 months after EOT	

Table 2 - Theoretical Schedule of Visits and Acceptable Leeway

* The acceptable leeway for the visits starts on the first day of the period mentioned and ends on the last day of the period mentioned.

For the purposes of the study, patients will be hospitalised from their arrival at the hospital/investigational centre until D18. They will be permitted to leave hospital from D11 onwards, if their clinical status allows it.

Any additional unscheduled visits that may take place must be recorded in the CRF.

6.2. Screening and Baseline Assessment

6.2.1. Diagnosis of HAT

The mobiliser of the mobile team will inform the communities in the villages of the HAT screening activities, as is usually the case (see Section 14.1 Information of Communities; p71). Specific information concerning the study should be provided to the community, i.e. a brief description of the aim of the study, explanation of the process for collecting informed consent, duration and importance of follow-up.

HAT case detection may be carried out by a mobile team.

A physical examination and, potentially, tests may be performed to collect sufficient information to suggest a diagnosis of HAT. Whenever possible, CSF sampling will be performed at the investigational centre, or by the mobile team of the National HAT Control Programmes (see Section 4.1. Enrolment/Inclusion Procedures; p 33).

6.2.2. Pre-screening and Screening

The following assessments will be performed to confirm the diagnosis of HAT, to collect medical history and to check the inclusion and exclusion criteria.

- Sampling to test for trypanosomes in the blood using Woo test/CTC, thick and thin blood smears, mAECT and mAECT-BC with INRB kits, as well as in fresh lymph node aspirate (detection using microscopy);
- CSF sampling for diagnosis and staging of HAT based on WBC and detection of trypanosomes using Fuchs-Rosenthal/Fast-Read 102® counting chamber and Modified Single Centrifugation (MSC) with INRB kits;
- Collection of full medical history;
- Demographic data and prior treatment;
- Karnofsky Performance Score, body weight, height and vital signs including body temperature, blood pressure, heart rate and respiratory rate;
- Screening for malaria using RDT and/or thick blood smear;
- Review of inclusion and exclusion criteria;
- Digital ECG recording (CarTouch®): the recordings will be transmitted electronically for centralised reading. The central cardiologist will review the ECG and prepare a report, which will then be sent to the Investigator, stating whether or not the patient can be included in the study.

6.2.3. Baseline Assessment

The following assessments will be performed to assess the patient's baseline status and confirm the patient's eligibility to participate in the study just before the start of treatment.

- Review of inclusion and exclusion criteria;
- Karnofsky Performance Score;
- Vital signs including body temperature, blood pressure and heart rate;
- Verification of clinical signs and symptoms of HAT;
- Physical and neurological examinations;
- Collection of concomitant treatment;
- Urine pregnancy test for girls ≥12 years of age;
- Laboratory safety assessments (see Appendix 3 Laboratory Tests; p 90)
 whenever possible, all laboratory tests will be performed on fasting patients:

- o Haemoglobin,
- Haematology: WBC, platelet count,
- Biochemistry: albumin (ALB), alkaline phosphatase (ALP), alanine aminotransferase (ALAT), aspartate aminotransferase (ASAT), blood urea nitrogen (BUN), chloride (CI-), creatinine (CRE), glucose (GLU), potassium (K+), sodium (Na+), calcium (Ca2+), total bilirubin (TBIL), bicarbonates (tCO₂) and total protein (TP),
- Urine analysis, i.e. WBC, pH, protein, urobilinogen, blood, nitrites, glucose, ketone bodies and bilirubin;
- Digital ECG recording (CarTouch®): triplicate tracings to assess QT interval. The recordings will be transmitted electronically for centralised reading of QT interval.

If the assessments mentioned in Section 6.2.2, i.e. haemoglobin, haematology, biochemistry and urine analysis, were performed within 4 days prior to the first administration, the findings will be considered as baseline values and the tests will not be repeated at the Baseline Assessment.

6.3. Assessments during Hospitalisation

6.3.1. Efficacy, Clinical Signs and Symptoms

Patients will be questioned regarding potential adverse events every day during hospitalisation and then at each subsequent visit (see Section 6.5 Safety Assessments, Definitions and Reporting of Adverse Events; p51).

- Physical examination and neurological assessment, including signs and symptoms of HAT, performed only at baseline and on D11, will be performed prior to intake of fexinidazole (D-1/D1) and on D5, D8, D11 (EOT visit) and between D13 and D18 (EOH visit)
- Testing for *T.b. gambiense* in blood, lymph and CSF at the EOT visit (D11). Testing for parasites in the CSF will be performed only in the first 30 patients, except if a failure is observed among these 30 patients.
- Lymph node biopsy at the EOT and at subsequent assessments is not recommended unless the Investigator considers that the procedure carries no risk for the patient.

